### **10.1 Summary Tables for Taste Questionnaire Assessments**

Acceptability of taste (overall liking of product) will be summarised (i.e., n, mean, SD, median, minimum and maximum) by treatment.

For each of the taste attributes described above, the number and percentage of subjects who selected each taste rating on the 9-point scale and/or N/A will be summarised by treatment. The safety population will be used as the denominator in the calculation of percentages.

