# **6 Populations and Analysis Sets**

## **6.1 Safety Population and Safety Analysis Set**

The safety population and safety analysis sets will be defined separately for each study part.

The safety population will include all subjects who have received any amount of IMP.

The safety analysis set will be defined on a treatment basis and will include all safety data from the subjects included in the safety population who have received that treatment.

The safety population will be confirmed by Quotient with approval from MMV after database lock (Part 2) and prior to unblinding (Part 1 and Part 3) and will be summarised for the populations table and to determine the subjects to be included in the safety analysis set.

The safety analysis set will be confirmed by Quotient with approval from MMV at the same time as the relevant safety population and will be summarised for the analysis of demographic and baseline characteristics, and all safety data.

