## **6.2 Taste Population and Taste Analysis Set**

The taste population will include all subjects who have received at least one regimen (i.e., active dose or placebo), in Part 1, and held it in their mouth for approximately 10 to 15 seconds. Participants will have also completed the taste questionnaire for a regimen and have no relevant protocol deviations for any taste test or AEs which confound the taste assessment.

The taste population will be determined by Quotient with approval from MMV after database lock and will be used for the taste tables and to determine the participants to be included in the taste analysis set.

---

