**Sponsor/Quotient Sciences Confidential**

---

The taste analysis set will be defined on a regimen basis and will include all relevant data from the participants included in the taste population who have received that test product.

The taste analysis set will be determined by Quotient with approval from MMV at the same time as the taste population and will be used for all summary tables and formal statistical analysis of taste data.

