**Sponsor/Quotient Sciences Confidential**

Medicines for Malaria Venture  
Protocol: MMV\_MMV367\_21\_01

Page x of y

TABLE 14.6.1.1  
Taste Assessments: Taste Aspect  
Summary Statistics: Taste Analysis Set  
Part 1

<Taste Aspect>

MMV367

Statistic	Pooled Placebo (N=XX)	100 mg (N=XX)	300 mg (N=XX)	....
n	xx	xx	xx	...
Mean	xx.x	xx.x	xx.x	...
SD	xx.x	xx.x	xx.x	...
Median	xx.x	xx.x	xx.x	...
Min	xx.x	xx.x	xx.x	...
Max	xx.x	xx.x	xx.x	...
GRADE 1 n (%)	xx (xx.x)	xx (xx.x)	xx (xx.x)	...
GRADE 2 n (%)	xx (xx.x)	xx (xx.x)	xx (xx.x)	...
GRADE 3 n (%)	xx (xx.x)	xx (xx.x)	xx (xx.x)	...
GRADE 4 n (%)	xx (xx.x)	xx (xx.x)	xx (xx.x)	...
GRADE 5 n (%)	xx (xx.x)	xx (xx.x)	xx (xx.x)	...
GRADE 6 n (%)	xx (xx.x)	xx (xx.x)	xx (xx.x)	...
GRADE 7 n (%)	xx (xx.x)	xx (xx.x)	xx (xx.x)	...
GRADE 8 n (%)	xx (xx.x)	xx (xx.x)	xx (xx.x)	...
GRADE 9 n (%)	xx (xx.x)	xx (xx.x)	xx (xx.x)	...

Note: The data in this table are presented in listing xx

All subjects were planned to receive a single dose of either MMV367 or matching placebo

All Placebo/All Active relate to placebo or active subjects pooled over all cohorts, respectively

Key for grade: 1=Dislike extremely, 2=Dislike very much, 3=Dislike moderately, 4=Dislike slightly, 5=Neither like nor dislike, 6=Like slightly, 7=Like moderately, 8=Like very much, 9=Like extremely

PROGRAM PATH: X:\~\QSC207031\~\TFLS\PRODUCTION\TAB-XX

DDMMYYYY HH:MM

Programming note: This table will be continued for all dose levels.

A separate page will be used for each taste aspect with the relevant subheading

A similar table will be produced for Overall Acceptability, i.e., Table [14.6.1.2]

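### The denominator named in SAP 10.1 for taste percentages (safety population) conflicts with the set the tables are built on (taste analysis set), so percentages are understated if any dosed participant is excluded

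*SAP*

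**What the plan says.** SAP 10.1 plans, for each taste attribute, the number and percentage of participants "who selected each taste rating on the 9-point scale and/or N/A will be summarised by treatment". The next sentence fixes the denominator: "The safety population will be used as the denominator in the calculation of percentages."

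Three other places in the SAP assign these tables to a different set.

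- SAP 6.2 says that the taste analysis set "will be used for all summary tables and formal statistical analysis of taste data". It adds: "The taste analysis set will be defined on a regimen basis."
- The index of tables (SAP section 18) lists Tables 14.6.1.1 and 14.6.1.2 under the taste analysis set.
- Mock Table 14.6.1.1 is headed "Summary Statistics: Taste Analysis Set" and carries an N for pooled placebo and for each dose level.

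The two sets are not the same by definition. Under SAP 6.1, "The safety population will include all subjects who have received any amount of IMP." Under SAP 6.2, a participant must also have held the dose in the mouth for about the specified time, completed the questionnaire, and "have no relevant protocol deviations for any taste test or AEs which confound the taste assessment".

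**The concern.** A programmer cannot follow the denominator sentence in SAP 10.1 and also match the title and column N of the mock table whenever the two sets differ. A participant left out of the taste set contributes no rating to the numerator but still counts in the denominator. Every rating percentage in that column is then too low, and the column falls short of 100%. Columns with different numbers of exclusions are deflated by different factors, which weakens the comparison across dose levels that the table exists to show.

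The rule also departs from the SAP's practice elsewhere. The denominators for demographics (SAP 7.5) and adverse events (SAP 11.3.1) are the safety analysis set on which those tables are built. The QTc categories (SAP 11.6.1) use participants measured at that time point.

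A smaller gap sits in the same table. SAP 10.1 plans to count N/A, and the questionnaire in Protocol Appendix 9 offers N/A for each attribute, but mock Table 14.6.1.1 has rows for grades 1 to 9 only. Any N/A response would leave the printed rows short of 100% under either denominator.

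**Working it through.** The documents state no taste percentage and no expected number of taste exclusions, so there is no plan figure to reproduce.

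**Inputs**

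- Dose column: n = 6 on active (SAP 5.1.1).
- Pooled placebo: 2 per cohort, so n = 2 × 4 = 8 with four cohorts and 2 × 5 = 10 if optional Cohort 1E runs (SAP 5.1.1).
- Participants dosed but excluded from the taste set in that column: k = 0, 1 or 2. This is an assumed range.

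**Formulas, counting the safety population within treatment**

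- One participant on the taste-set basis: 100 / (n − k).
- One participant on the safety-population basis: 100 / n.
- Column total on the safety-population basis, if everyone in the taste set has a tabulated response: 100 × (n − k) / n.

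**Results**

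| Column | k | One participant, taste set | One participant, safety population | Column total, safety population |
|---|---|---|---|---|
| Dose, n = 6 | 0 | 1/6 = 16.7% | 1/6 = 16.7% | 6/6 = 100% |
| Dose, n = 6 | 1 | 1/5 = 20.0% | 1/6 = 16.7% | 5/6 = 83.3% |
| Dose, n = 6 | 2 | 1/4 = 25.0% | 1/6 = 16.7% | 4/6 = 66.7% |
| Pooled placebo, n = 10 | 1 | 1/9 = 11.1% | 1/10 = 10.0% | 9/10 = 90.0% |
| Pooled placebo, n = 10 | 2 | 1/8 = 12.5% | 1/10 = 10.0% | 8/10 = 80.0% |
| Pooled placebo, n = 8 | 1 | 1/7 = 14.3% | 1/8 = 12.5% | 7/8 = 87.5% |
| Pooled placebo, n = 8 | 2 | 1/6 = 16.7% | 1/8 = 12.5% | 6/8 = 75.0% |

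As an example, take a dose column with one exclusion in which three participants choose the same rating. On the taste set that is 3/5 = 60.0%. Under the SAP 10.1 rule it is 3/6 = 50.0%, printed beneath a column header that, for a table on the taste analysis set, would give N = 5.

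**The case against.** The best defence is that the difference may be zero. SAP 10.1 asks for summaries by treatment immediately before the denominator sentence, and mock Table 14.1.2.1.2 counts the safety population by placebo and dose, so a within-treatment denominator is the natural reading. The protocol also makes exclusions less likely. Staff observe the taste test (Protocol 11.2), people with conditions affecting smell or taste are not enrolled in Part 1 (Protocol 9.3, criterion 9), and every Part 1 participant is to complete the questionnaire within 10 minutes (Protocol 13.3). All of this stands. It makes the effect conditional but does not remove the conflict, because SAP 6.2 expressly allows for exclusions.

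A second defence is that the table prints counts and N beside the percentages, so a reader can recompute them, and that SAP section 16 lets mock tables be adjusted. The first part is fair and limits the harm. The second covers the missing N/A row, but a denominator stated in the text is not a matter of labelling or appearance.

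A reader might also infer something stronger from SAP 6.1, which says: "The safety population and safety analysis sets will be defined separately for each study part." Taken literally, the denominator would be all of Part 1. With five cohorts of 8 that is 40, and a complete dose column would sum to only 6/40 = 15.0%. The documents do not support relying on that figure. SAP 7.5 and 11.3.1 also name a whole set as denominator for tables that are plainly split by dose, and dividing a column of six by 40 would contradict the column N in mock Table 14.6.1.1.

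**Conclusion.** The inconsistency is real, and nothing else in the SAP resolves it. It is a stated rule that conflicts with the set named for the table, not a missing detail. Its effect depends on two things: whether any dosed participant is left out of the taste set, and how the safety population is counted. Counting within treatment, a dose column of six loses 16.7 percentage points from its total for each exclusion (100% to 83.3% to 66.7%). With no exclusions the percentages are identical. The exclusion counts are assumptions.

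It would go too far to say that the percentages are bound to be wrong, or that a taste conclusion is at risk. The objective is exploratory, and its endpoint (SAP section 4) is the questionnaire score, not the distribution of ratings. The mean, SD and median, the box and bubble plots, and the Hodges-Lehmann and Wilcoxon comparison in mock Table 14.6.1.3 use no percentages. This is a minor correction, worth making because it is easy and removes an ambiguity before programming.

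**What to change.** In SAP 10.1, replace the denominator sentence with: *The denominator is the number of participants in the taste analysis set for that treatment.* For the placebo column this means the taste-set placebo participants pooled over cohorts, as the mock table already shows them. That brings 10.1 into line with 6.2, the table index and the column N.

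In mock Table 14.6.1.1, add a row for N/A, which 10.1 already plans to summarise, and a row for any missing response. The categories then sum to 100% of the column N.

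The cost is one sentence and two mock-table rows. No data collection, analysis set or inferential method changes.

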### **10.2 Listings for Taste Questionnaire Assessments**

All taste assessments data will be listed.

### **10.3 Statistical Figures for Analysis of Taste Questionnaire Data**

In Part 1, to complement to assessment of the taste questionnaire data, boxplots of each dose level will be produced separately for each taste attribute and overall acceptability. Dose level will be plotted on the X axis and taste assessment score will be plotted on the Y axis (i.e., 1=Dislike extremely, 2=Dislike very much etc.).

Additionally, bubble plots of each taste attribute and overall acceptability will be produced. Each dose level will be plotted on the X axis, with the assessment score plotted on the Y axis. Each bubble will contain a count of the number of subjects which scored a particular outcome. The size of the bubble will reflect the count (i.e., The bubble associated with the most popular score will be the biggest).

## **11 Safety Assessments**

Safety data summaries will be presented by actual treatment and the safety analysis set will be used throughout.

### **11.1 Extent of Exposure and Treatment Compliance**

The number and percentage of subjects dosed with IMP (each day, Part 3 only), will be presented for all placebo, all active, and each active dose level separately in Part 1 and Part 3, and by treatment received in Part 2.

Dosing details (including the date and time of all IMP administrations and any comments) will be listed for all enrolled subjects. Any recorded deviations from the planned dosing regimen will be listed as protocol deviations. Total number of days of exposure and measures of compliance will be included in the listing (Part 3 only).

---

**Sponsor/Quotient Sciences Confidential**

---

**11.2 Meal Details**

For Part 2 only, meal details as recorded on the electronic case report form (eCRF) will be listed for all enrolled subjects. Any recorded deviations from the planned mealtimes will be listed as protocol deviations.

**11.3 Adverse Events**

Throughout the study, all AEs will be evaluated by the PI and noted in the AE section of the eCRF. An AE is any untoward medical occurrence in a participant that occurs either before dosing (referred to as a pre-dose AE) or once a medicinal product has been administered, including occurrences which are not necessarily caused by or related to that product.

AEs will be coded using the Medical Dictionary for Regulatory Activities MedDRA v25.0 (or more recent version), and reported by SOC and PT.

AEs will be classified into the following categories:

- Pre-dose AEs: AEs recorded at screening or with a start date and time prior to the first dose of IMP
- Treatment-emergent AEs (TEAEs): AEs that commence during/after the first dose of IMP or commence before first dose of IMP (i.e., a pre-dose AE or existing medical condition) but worsen in intensity during exposure to IMP

For Part 2 only, TEAEs will be assigned to the treatment of the period in which the AE first occurred. Where the severity of an AE intensifies or symptoms change in a subsequent period, this will be defined as a new AE and included under the regimen associated with the subsequent period. Adverse events that occur during the washout period will be assigned to the treatment the participant received during the period immediately before the washout period.

Adverse events will be classified as “mild,” “moderate” or “severe” when considering their severity

Adverse events will be classified as “unrelated”, or “related” when considering their relationship to IMP. TEAEs classified as “related”, will be defined as IMP-related events. Pre-dose AEs will always have the classification of “unrelated”

If the severity or relationship to IMP of a TEAE is missing, the severity/relationship will be tabulated as “missing” in the summary tables

When summary presentation is made by maximum severity, “missing” will be handled as follows:

- If there are other events (i.e., same SOC and PT code) with a maximum severity recorded as “moderate” or “severe” for that participant and regimen, then the maximum observed severity for that participant will be categorised and presented as “moderate” or “severe”, respectively
- If there are other events (i.e., same SOC and PT code) with a maximum severity recorded as “mild” for that participant and regimen, then the maximum observed severity for that participant will be categorised and presented as “missing”

---

**Sponsor/Quotient Sciences Confidential**

---

When summaries are presented by relationship to IMP, “missing” will be handled as follows:

- If there are other events (i.e., same SOC and PT code) with a most closely related association recorded as “related” for that participant and regimen, then the maximum observed relationship for that participant will be categorised and presented as “related”, respectively
- If there are other events (i.e., same SOP and PT code) with a most closely related association recorded as “unrelated” for that participant and regimen, then the maximum observed relationship for that participant will be categorised and presented as “missing”

Where the start date of an AE is missing and the stop date is on or after the day of first dose of IMP or both the start and stop dates are missing then a “worst-case” scenario will be assumed i.e., the AE is assumed to have occurred post-dose and is therefore considered treatment-emergent. If a partial start date/time is available then the event will be considered as treatment-emergent unless the partial information suggests otherwise.

### **11.3.1 Summary Tables for Adverse Events**

All pre-dose AEs (as defined in [Section 11.3](#)) will be excluded from the summary tables but will be listed for all enrolled subjects.

Descriptive statistical methods will be used to summarise the TEAE data.

For each study part, the number and percentage of subjects reporting each TEAE will be presented for both SOC and PT. For summaries by SOC and PT, with the exception of TEAEs by severity and relationship to IMP, the number of subjects and the number of events will be summarised. For summaries by severity and relationship only the number of subjects will be summarised.

For counts of subjects experiencing events the following will apply:

#### Part 1 and Part 3:

- A participant with a TEAE in more than one body system will be counted once in the total number of subjects with TEAEs
- A participant with more than 1 TEAE in the same SOC counts only once at the SOC level
- A participant with more than 1 TEAE in the same PT counts only once at the PT level

#### Part 2:

- A participant experiencing TEAEs in more than one body system, within a period, will be counted once in the total number of subjects with TEAEs in that period
- A participant with more than 1 TEAE in the same SOC, within a period, counts only once at the SOC level
- A participant with more than 1 TEAE in the same PT, within a period, counts only once at the PT level

For event counts, all events are included.

**Sponsor/Quotient Sciences Confidential**

---

When it is necessary to calculate percentages, the denominator will be the total number of subjects in the safety analysis set (and period – Part 2 only), and the numerator will be the total number of subjects reporting a TEAE within the relevant category.

Summaries presented for SOC and PT will be presented in descending order of frequency overall i.e., most frequently reported SOC in the study part and then by most frequently reported PT in the study part within each SOC.

#### **11.3.1.1 Overall Summary of Adverse Events**

The following will be summarised by treatment and overall, in Part 2, and by all placebo, all active, and each dose level in Part 1 and Part 3 for the safety analysis set:

- Number and percentage of subjects reporting at least 1 TEAE
- Number and percentage of subjects reporting severe TEAEs
- Number and percentage of subjects reporting IMP-related TEAEs
- Number and percentage of subjects reporting serious TEAEs
- Number and percentage of subjects reporting TEAEs leading to participant withdrawal
- Number and percentage of subjects reporting TEAEs leading to death
- Total number of TEAEs
- Total number of severe TEAEs
- Total number of IMP-related TEAEs
- Total number of serious TEAEs
- Total number of TEAEs leading to participant withdrawal
- Total number of TEAEs leading to death

#### **11.3.1.2 Summary of Treatment-Emergent Adverse Events**

All subjects reporting TEAEs will be summarised by treatment and overall in Part 2, and by all placebo, all active and each dose level in Part 1 and Part 3. Counts will be given for number of subjects and number of events. Subjects experiencing more than 1 TEAE treatment will be counted only once for number of subjects but will be counted more than once for number of events.

Additionally, subjects reporting TEAEs will be summarised for SOC and PT by treatment and overall in Part 2, and by all placebo, all active and each dose level in Part 1 and Part 3. Counts will be given for number of subjects and number of events. Subjects experiencing more than 1 episode of a TEAE within a treatment will be counted only once within each SOC and PT using the most severe episode.

#### **11.3.1.3 Summary of Treatment-Emergent Adverse Events by Severity**

All subjects reporting TEAEs will be summarised by severity (i.e., mild, moderate or severe) and by treatment in Part 2, and by all placebo, all active and each dose level in Part 1 and Part 3. Counts will be given for number of subjects, not number of events. Counts will be given by maximum severity (i.e., subjects experiencing more than 1 TEAE within a treatment will be counted only once using the most severe episode).

**Sponsor/Quotient Sciences Confidential**

---

Additionally, subjects reporting TEAEs will be summarised for SOC and PT by maximum severity (i.e., mild, moderate or severe) and by treatment in Part 2, and by all placebo, all active and each dose level in Part 1 and Part 3. Counts will be given for total number of subjects, not for events. Counts by maximum severity will be given (i.e., subjects experiencing more than 1 TEAE within a treatment will be counted only once within each SOC and PT using the most severe episode).

**11.3.1.4 Summary of Treatment-Emergent Adverse Events by Relationship to IMP**

All subjects reporting TEAEs will be summarised by relationship to IMP (i.e., unrelated, or related) and by treatment in Part 2, and by all placebo, all active and each dose level in Part 1 and Part 3. Counts will be given for number of subjects, not number of events. Counts will be given by the closest relationship to IMP (i.e., subjects experiencing more than 1 TEAE within a treatment will be counted only once using the most closely related event).

Additionally, subjects reporting TEAEs will be summarised for SOC and PT by closest relationship to IMP (i.e., unrelated or related) by treatment in Part 2, and by all placebo, all active and each dose level in Part 1 and Part 3. Counts will be given for total number of subjects, not for events. Counts by closest relationship will be given (i.e., subjects experiencing more than 1 TEAE within a treatment will be counted only once within each SOC and PT using the most closely related event).

**11.3.1.5 Summary of IMP-related Treatment-Emergent Adverse Events by System Organ Class and Preferred Term**

All subjects reporting IMP-related TEAEs will be summarised by treatment in Part 2, and by all placebo, all active and each dose level in Part 1 and Part 3. Counts will be given for number of subjects and number of events. Subjects experiencing more than 1 IMP-related TEAE within a treatment will be counted only once for number of subjects but will be counted more than once for number of events.

Additionally, subjects reporting IMP related events will be summarised for SOC and PT by treatment in Part 2, and by all placebo, all active and each dose level in Part 1 and Part 3. Counts will be given for number of subjects and number of events. Subjects experiencing more than 1 episode of an IMP-related TEAE within a treatment will be counted only once within each SOC and PT using the most severe episode.

